9.2.3 Exclusion criteria

Patients meeting any of the following exclusion criteria (see Annex 3: Additional information) will be excluded from the analysis:

• A verified ambulatory or primary/ secondary hospital discharge diagnosis of valvular atrial fibrillation in the baseline period;

- A verified ambulatory or primary/ secondary hospital discharge diagnosis indicating pregnancy in the baseline period;
- A verified ambulatory or primary/ secondary hospital discharge diagnosis of a transient cause of atrial fibrillation in the baseline period;
- A verified ambulatory or primary/ secondary hospital discharge diagnosis of venous thromboembolism (VTE) in the previous or same quarter of the index date;
- A claim for hip or knee replacement surgery in the 60 days prior to or on the index date;
- A prescription of heparin or fondaparinux in the 60 days prior to or on the index date;
- A prescription of more than one oral anticoagulant (rivaroxaban, apixaban, edoxaban or phenprocoumon) on the index date;
- A prescription of warfarin or dabigatran in the baseline period or on the index date;
- A verified ambulatory or primary/ secondary hospital discharge diagnosis of end-stage kidney disease or a claim for dialysis in the baseline period;
- Patients receiving an initial dose of rivaroxaban 10 mg/ 2.5 mg or edoxaban 15 mg (these dosages are not indicated for the treatment of NVAF).
- A prescription of contraindicated drug for apixaban or rivaroxaban due to drug interactions (i.e. azole antifungals and HIV protease inhibitors) in the 60 days before or on the index date.

For the main analysis, patients will be followed from the index date until the first diagnosis of the respective outcome event, discontinuation of the index drug, death, end of continuous insurance in the SHI or the end of the study period (31 December 2017), whichever comes first. Patients will be censored in all analyses if they switch to phenprocoumon or another NOAC (including dabigatran), receive a prescription of heparin/ fondaparinux, warfarin, rivaroxaban 10 mg/ 2.5 mg, edoxaban 15mg or a contraindicated drug as defined above. For specific analyses, the end of follow-up may differ as described in 9.3.1.

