9.3.3 Covariate definition

All demographic and clinical characteristics will be assessed based on primary and secondary hospital diagnoses and verified ambulatory diagnoses (ICD-10 GM codes), OPS codes, EBM codes and ATC codes as defined in Annex 3: Additional information. Unless otherwise mentioned, all information on covariates will be collected in the baseline period., i.e. in the 365 days prior to the index date). The assessment date for hospital diagnoses will be the admission date of the respective hospitalization and for ambulatory diagnoses the date of the first encounter with the diagnosing physician in the respective quarter (as ambulatory diagnoses are available on a quarterly basis only). Data derived from OPS codes and EBM codes will be assessed on the exact date.

Demographic characteristics

- Gender at index date
- Age at index date
- Age at index date categorized: 18–39, 40–44, 45–49, ..., 85-89, 90+ years

Clinical characteristics

- CHADS₂ score
- CHA₂DS₂-VASc score
- modified HAS-BLED score (the INR will not be included in the calculation of the score because this information is not available in the InGef database, end-stage renal disease will not be considered as these patients will be excluded from the analysis)
- Comorbidities
 - o Alcohol abuse
 - o Anemia
 - Aortic plaque
 - o Anemia
 - Coronary heart disease
 - Angina pectoris
 - Myocardial infarction
 - Acute ischemic heart diseases
 - Chronic ischemic heart disease
 - Coronary artery bypass graft(s)
 - Percutaneous coronary intervention
 - o Dementia
 - o Depression
 - o Diabetes mellitus
 - o Drug abuse
 - o Gastric or peptic ulcer disease/diseases of gastrointestinal tract
 - o Heart failure
 - History of major bleeding (hospitalization only)
 - o Hypertension
 - Hypothyroidism

- o Inflammatory bowel disease
- IS or transient ischemic attack
- Other cerebrovascular disease
- o Liver disease
- o Hyperlipidemia
- o Volume depletion
- Other metabolic disorders
- o Obesity
- Peripheral arterial disease
- o Psychosis
- o Pulmonary disease
- o Rheumatoid arthritis/collagen vascular disease
- Tobacco abuse
- o Other vascular disease
- Malignant cancer (except non-melanoma skin cancer)
- Comedications
 - o Angiotensin-converting enzyme inhibitors or angiotensin-receptor blockers
 - o Antiarrhythmics
 - o Antidepressants
 - o Antiplatelets
 - Antiulcer drugs (except proton-pump inhibitors)
 - o Calcium channel blockers
 - o Diabetes drugs
 - o Diuretics

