9.3.4 Subpopulations and Subgroups

Subgroups and subpopulation are only build on the basis of conditions already present at index date.

The following subpopulations of special interest will be defined:

• Patients with renal impairment initiating either phenprocoumon or reduced doses of NOACs

Patients with renal impairment will be identified based on primary and secondary hospital diagnoses or verified ambulatory diagnoses in the baseline period according to Fleet et al. (9) and Nielsen et al. (4) (see definition of renal impairment as covariate in Annex 3: Additional information).

• Patients with chronic renal disease initiating either phenprocoumon or reduced dose of NOACs

Patients with chronic renal disease will be identified based on primary and secondary hospital diagnoses or verified ambulatory diagnoses (ICD 10 GM code N18.3 and N18.4) in the baseline period.

The following subgroups of special interest will be defined. Analyses will be conducted also including a test for effect modification (interaction):

• Frail patients

Frailty can be operationalized in several ways, but is commonly characterized by a set of signs and symptoms in geriatrics and gerontology research. While difficult to assess in administrative claims data, the recently validated claims based Frailty Indicator (10) will be used in this study. This algorithm is

validated using against the frailty phenotype, which is the most widely used instrument for assessing frailty. The frailty cut-off for this study will be 0.25 as the desire is to specifically identify frail individuals.

• Age group (<=79 vs. 80+ years)

Age will be assessed at the index date.

• Renal impairment

Patients with renal impairment will be identified based on primary and secondary hospital diagnoses or verified ambulatory diagnoses in the baseline period according to Fleet et al. (9) and Nielsen et al. (4) (see definition of renal impairment as covariate in Annex 3: Additional information).

• Prior IS or SE

Patients with IS, TIA or SE will be identified based on primary and secondary hospital diagnoses or verified ambulatory diagnoses in the baseline period according the definition for IS/TIA and SE as covariate (see Annex 3: Additional information).

• Reduced vs. standard dose of NOACs

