9.4 Data sources

This study will be conducted based on the InGef (former HRI) database which is an anonymized healthcare claims database covering all geographic regions of Germany. It includes longitudinal data from approx. 6.7 million Germans insured in one of approx. 64 German SHIs currently contributing data to the database (mainly company or guild health insurances).

Claims data are transferred directly from health care providers to a specialized data center owned by SHIs, which provides data warehouse and IT services. In the data center (acting as a trust center), data is anonymized before entering the InGef database. Data are anonymized with respect to individual insured members, health care providers (e.g. physicians, practices, hospitals, pharmacies), and the respective SHI. The most important data elements included in the database are displayed in Table 2. The time period covered by the database is limited to a look-back period of 6 years starting with the most current complete year of data (11).

Table 2 Information included	in the InGef Database
-------------------------------------	-----------------------

Demographics

Gender

Age

Date of death

	Region for place of living				
	Insurance status (e.g. retired, family insurance)				
	Date of insurance start and end (observation period)				
Outpatient Care	Diagnosis (ICD 10-GM Codes) and quarter in which the diagnosis was documented				
	Procedures performed (e.g. laboratory, radiology, echocardiography) (EBM-Codes) and day of performance				
	Type of specialist that documented the diagnosis and performed the procedure (e.g. cardiologist, general practitioner)				
	Costs of outpatient care				
Pharmacy	Drug dispensed by central pharmaceutical number (package level) – this is mapped to ATC codes and DDD's by InGef				
	Quantity dispensed				
	Day of prescription				
	Day of dispensing				
	Type of doctor prescribing (e.g. cardiologist, general practitioner)				
	Costs of drugs dispensed from SHI perspective (without individual rebates between single sickness funds and pharmaceutical companies)				
Hospital care	Main diagnosis (ICD 10-GM Codes) and additional diagnoses				
	Performed procedures and surgeries (e.g. pacemaker implant, implantable cardioverter defibrillator				
	Date of hospital admission				
	Reason for admission (e.g. accident, emergency, normal)				
	Date of end of hospital stay				
	Reason of end of hospital stay (e.g. death in hospital, normal end)				

	DRG-Code			

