9.7.3 Sensitivity analysis

We will conduct three pre-defined sensitivity analyses to prove the consistency of our results. First, we will repeat the Cox regression analysis for IS/ SE as combined endpoint and ICH (primary objectives) as well as for the analysis of treatment discontinuation allowing for stockpiling of phenprocoumon and NOACs, i.e. if a prescription of the index drug is refilled before the estimated end of supply, the remaining supply of the prescription will be added to following prescription. Second, we will perform the Cox regression analysis for the outcomes ICH, IS, SE, severe IS, kidney failure, AKI and fatal bleeding excluding patients with a prior outcome event in the baseline period, i.e. major bleeding for ICH and fatal bleeding, IS or SE for IS and severe IS, SE (see covariate definition in Annex 3: Additional information). Third, we will repeat the Cox regression analysis for IS/ SE as combined endpoint and ICH analyses using the pDDD to calculate the supply for phenprocoumon as defined in section 9.3.1.

No actions will be taken to deal with missing data, since data from all dimensions is assumed to be complete.

All analysis will be performed using SAS Enterprise guide version 7.1 or R.

The statistical concept of the study described above will be supplemented by the more detailed statistical analysis plan.

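### Dating quarter-only ambulatory diagnoses to the quarter's first visit lets some codes added after the index date, including codes for early outcome events, count as baseline history

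*Protocol*

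**What the plan says.** All places are in the protocol.

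- **Data.** Table 2 in section 9.4 lists for outpatient care "Diagnosis (ICD 10-GM Codes) and quarter in which the diagnosis was documented"; no day is held.
- **Dating rule.** Section 9.3.3 gives the reason, "as ambulatory diagnoses are available on a quarterly basis only", and sets the date as "for ambulatory diagnoses the date of the first encounter with the diagnosing physician in the respective quarter". Unless otherwise stated, "all information on covariates will be collected in the baseline period., i.e. in the 365 days prior to the index date".
- **Requirement on subgroups.** Section 9.3.4: "Subgroups and subpopulation are only build on the basis of conditions already present at index date". For the prior-event subgroup it then says "Patients with IS, TIA or SE will be identified based on primary and secondary hospital diagnoses or verified ambulatory diagnoses in the baseline period".
- **Prior-event exclusion.** The second sensitivity analysis in section 9.7.3 repeats the Cox models for ICH, IS, SE, severe IS, kidney failure, AKI and fatal bleeding, "excluding patients with a prior outcome event in the baseline period", and points to the covariate definitions in Annex 3.
- **Codes (Annex 3).** The outcomes IS, SE and AKI are I63, I74 and N17. The same codes appear in the history definitions for IS/TIA, SE and AKI. I63 also feeds the stroke items of CHADS2, CHA2DS2-VASc, HAS-BLED and the frailty indicator.
- **Outcome dates.** Section 9.3.2 dates hospital-defined outcomes at admission.
- **VTE.** Section 9.2.3 excludes patients with a diagnosis of "venous thromboembolism (VTE) in the previous or same quarter of the index date".

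No section sets index-quarter ambulatory codes aside, and the limitations in section 9.9 do not mention the issue.

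**The concern.** A new user has often seen a physician shortly before the first dispensing. If that visit falls in the index quarter, it becomes the date of every diagnosis the same physician codes in that quarter, including those coded after the index date.

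A constructed case shows the consequence: visit on 5 January, index dispensing on 12 January, admission for ischemic stroke on 10 February, and the same physician codes I63 or I69.3 on 10 March. The rule dates that code 5 January. The February admission remains an outcome event. But the patient now also has a prior stroke, gains two CHA2DS2-VASc points, joins the 'Prior IS or SE' subgroup, and is removed from the second sensitivity analysis because of the very event it is meant to count.

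At stake are the prior-IS/SE subgroup and its interaction test, the stroke-based scores, and the sensitivity analysis for IS, SE, severe IS and AKI. Entry to the renal-impairment population is open in the same way, through N18.1-N18.4, N18.9 or N19 codes added after the index date.

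**Working it through.** **1. Reproduce Table 3 (section 9.5).** Expected IS/SE events = users × annual rate × 1 year.

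**2. Size the exposed window.** Assume index dates uniform within a quarter and a constant hazard. A quarter has 365.25/4 = 91.3 days, so on average 91.3/2 = 45.7 days remain after the index date, and 45.7/365.25 = 0.125 year. Exposed events = users × rate × 0.125.

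| Drug | Users × rate | Table 3 | In exposed window |
|---|---|---|---|
| Phenprocoumon | 35,400 × 0.025 = 885.0 | 885 | 110.6 |
| Apixaban | 16,800 × 0.027 = 453.6 | 454 | 56.7 |
| Rivaroxaban | 30,200 × 0.022 = 664.4 | 664 | 83.0 |
| Edoxaban | 1,600 × 0.022 = 35.2 | 35 | 4.4 |

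Table 3 reproduces. The window holds 12.5% of first-year events, about 255 over the four drugs. The share depends on follow-up. With the mean follow-up for ischemic stroke in Figure 1 (renal impairment, earlier study), it is at most about 45.7/219.56 = 21% or 45.7/415.4 = 11% for phenprocoumon, by exposure definition, and 45.7/347.27 = 13% for rivaroxaban 15 mg.

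**3. Allow for the unknown leak.** Let q be the share of exposed events that are coded, before the quarter ends, by a physician already seen in that quarter before the index date. The protocol gives no value for q.

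| q (assumed) | Phenprocoumon, 110.6 × q | Rivaroxaban, 83.0 × q | Share of events |
|---|---|---|---|
| 0.25 | 28 | 21 | 3.1% |
| 0.50 | 55 | 42 | 6.3% |
| 0.75 | 83 | 62 | 9.4% |

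**4. Effect when 'prior' events are excluded.** The hazard ratio (HR) is multiplied by (1 − 0.125·qT)/(1 − 0.125·qC), with T for the NOAC and C for phenprocoumon.

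- Equal q: factor 1.00.
- 0.25 against 0.50: 0.96875/0.9375 = 1.03.
- 0.25 against 0.75: 0.96875/0.90625 = 1.07. As an illustration, 0.86 (the rivaroxaban stroke/SE figure cited in section 7) would become 0.92.

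**5. Effect in a Cox model adjusted for prior IS.** A simulation used one data set of 100,000 patients per scenario, with true treatment HR 1, 15% with a true prior IS and a doubled hazard in those patients. Each pair is the same data set without and with the leak.

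| q (T, C) | Adjusted treatment HR | HR for prior IS | Treatment HR after exclusion |
|---|---|---|---|
| 0.50, 0.50 | 1.004 → 1.004 | 1.88 → 2.24 | 0.994 → 0.981 |
| 0.25, 0.50 | 1.052 → 1.053 | 1.93 → 2.20 | 1.053 → 1.088 |
| 0.25, 0.75 | 0.970 → 0.969 | 2.01 → 2.49 | 0.945 → 1.004 |

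Only the change within a row matters; departures from 1 before the arrow are sampling noise. The adjusted treatment HR stays put, the apparent effect of prior stroke is inflated, and the exclusion analysis moves mainly when leakage differs between groups. Propensity weights should also change little: for phenprocoumon the prior-stroke flag changes in 28/35,400 = 0.08% to 83/35,400 = 0.23% of patients.

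**The case against.** **Outcomes keep their dates.** A reader might infer that outcome events themselves are moved into baseline and lost from the main analysis. Section 9.3.2 rules this out: IS, SE, ICH and AKI are dated at hospital admission. Only a second, ambulatory code for the same event can move, and only if it comes from a physician already seen earlier in that quarter. This stands, and is why the point is that such codes can count as baseline.

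**The primary results are largely protected.** A reader might infer that the primary comparisons are biased. Combined IS/SE is not among the outcomes of the second sensitivity analysis. Its exclusion for ICH and fatal bleeding uses major-bleeding history, which is hospital-only; I60-I62 can enter only through HAS-BLED and the frailty item, whose tables state no such limit. The renal-impairment list contains neither N17 nor N18.5, so an AKI code or a stage-5 code admits nobody. A late renal code that does admit a patient does not by itself select on IS/SE or ICH. All of this stands.

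**The leak may be small.** Under the uniform model the mean time from an exposed event to quarter end is (91.3²/6)/(91.3/2) = 91.3/3 = 30 days. Within it the patient must be discharged and coded by the right physician. High values of q are therefore unsupported, as is any stated inflation of subgroup events, which would also need a prevalence and event rate for prior stroke that the protocol does not give.

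**The rule approximates what the data cannot show.** True, but the approximation always moves codes towards baseline, and section 9.3.4 states a requirement that it cannot meet. A later analysis plan may add detail, but the dating rule is fixed here.

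**Conclusion.** The point holds in limited form. As written, section 9.3.3 lets post-index ambulatory codes enter baseline in the index quarter, in conflict with section 9.3.4, and nothing else in the protocol repairs it.

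The harm falls on the prior-IS/SE subgroup and its interaction test, the stroke items of the scores, and the second sensitivity analysis for IS, SE, severe IS and AKI. Entry to the renal-impairment population is open to the same fault, but no figure in the protocol sizes it.

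About 12.5% of first-year IS/SE events are exposed (about 111 of 885 and 83 of 664), given uniform index dates, constant hazard and one year of follow-up. The fraction misdated is unknown. In the exclusion analysis an equal leak leaves the HR about unchanged. An unequal one could shift it by some 3% to 7% under the q values shown. Unequal leakage is conceivable because section 7 describes intensive monitoring under vitamin-K antagonists, but the size of any difference is not known. The effect on the main adjusted HRs and on ICH is expected to be small.

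The same-quarter VTE exclusion also uses days after the index date. It is a milder case, since VTE is not an outcome.

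**What to change.** 1. For the prior-IS/SE subgroup, the stroke items of the scores and the prior-event exclusions, do not use ambulatory codes from the index quarter. Use ambulatory codes only from quarters that ended before the index date and lie within the 12-month enrolled baseline, plus hospital diagnoses from stays discharged on or before the index date.
2. For renal impairment, chronic renal disease and the other covariates, keep the present rule and add a sensitivity analysis that drops index-quarter ambulatory codes. Dropping them from the main analysis would lose true confounders recorded at the prescribing visit.
3. Limit the same-quarter VTE exclusion to information dated on or before the index date, or test it in that sensitivity analysis.

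The window should not simply be four completed quarters. That can reach back up to 15 months (an index date of 30 June 2017 would need data from 1 April 2016), while section 9.2.2 requires only 12 months of enrollment.

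**Cost:** short additions to sections 9.2.3, 9.3.3, 9.3.4 and 9.7.3, a changed look-back in the programming and one more sensitivity run; no new data. Some true prior events first coded as outpatient in the index quarter will be missed. For most index dates only three whole quarters fit inside the 12 months, so the ambulatory look-back for these items becomes shorter.

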9.3.4 Subpopulations and Subgroups

Subgroups and subpopulation are only build on the basis of conditions already present at index date.

The following subpopulations of special interest will be defined:

• Patients with renal impairment initiating either phenprocoumon or reduced doses of NOACs

Patients with renal impairment will be identified based on primary and secondary hospital diagnoses or verified ambulatory diagnoses in the baseline period according to Fleet et al. (9) and Nielsen et al. (4) (see definition of renal impairment as covariate in Annex 3: Additional information).

• Patients with chronic renal disease initiating either phenprocoumon or reduced dose of NOACs

Patients with chronic renal disease will be identified based on primary and secondary hospital diagnoses or verified ambulatory diagnoses (ICD 10 GM code N18.3 and N18.4) in the baseline period.

The following subgroups of special interest will be defined. Analyses will be conducted also including a test for effect modification (interaction):

• Frail patients

Frailty can be operationalized in several ways, but is commonly characterized by a set of signs and symptoms in geriatrics and gerontology research. While difficult to assess in administrative claims data, the recently validated claims based Frailty Indicator (10) will be used in this study. This algorithm is

validated using against the frailty phenotype, which is the most widely used instrument for assessing frailty. The frailty cut-off for this study will be 0.25 as the desire is to specifically identify frail individuals.

• Age group (<=79 vs. 80+ years)

Age will be assessed at the index date.

• Renal impairment

Patients with renal impairment will be identified based on primary and secondary hospital diagnoses or verified ambulatory diagnoses in the baseline period according to Fleet et al. (9) and Nielsen et al. (4) (see definition of renal impairment as covariate in Annex 3: Additional information).

• Prior IS or SE

Patients with IS, TIA or SE will be identified based on primary and secondary hospital diagnoses or verified ambulatory diagnoses in the baseline period according the definition for IS/TIA and SE as covariate (see Annex 3: Additional information).

• Reduced vs. standard dose of NOACs

For each respective NOAC, patients will be classified into reduced and standard dose initiators. Analyses will be conducted comparing reduced dose initiators vs. phenprocoumon and standard dose initiators vs. phenprocoumon.

• Malignant cancer (excl. non-melanoma skin cancer)

Patients with malignant cancer (excl. non-melanoma skin cancer) will be identified based on primary and secondary hospital diagnoses or verified ambulatory diagnoses in the baseline period according the definition for malignant cancer as covariate (see Annex 3: Additional information). For the subgroup of patients with cancer, the different underlying cancer-types will additionally be included as covariates in the respective statistical models.

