8.3 Other objectives

Other objectives of this study are:

- To describe the risk of IS/ SE as combined effectiveness outcome in patients with NVAF (overall population as well as patients with renal impairment) initiating treatment with reduced dose of individual NOACs (rivaroxaban, apixaban, edoxaban) compared to standard dose in a subpopulation of patients without renal impairment
- To describe the risk of severe IS in patients with NVAF (overall population as well as patients with renal impairment) initiating treatment with reduced dose of individual NOACs (rivaroxaban, apixaban, edoxaban) compared to standard dose in a subpopulation of patients without renal impairment
- To describe the risk of fatal bleedings in patients with NVAF (overall population as well as patients with renal impairment) initiating treatment with reduced dose of individual NOACs (rivaroxaban, apixaban, edoxaban) compared to standard dose in a subpopulation of patients without renal impairment
- To describe the risk of intracranial hemorrhage (ICH) in patients with NVAF (overall population as well as patients with renal impairment) initiating treatment with reduced dose of individual NOACs (rivaroxaban, apixaban, edoxaban) compared to standard dose in a subpopulation of patients without renal impairment

9. **Research methods**

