9.7.2 Main analysis

Analyses will be conducted in line with good statistical practices. Models will use confounding factors to adjust for group differences. However, unmeasured confounding and resulting confounding bias affecting point estimates, confidence intervals and any p-values in the treatment group comparisons may remain.

In a first step, Cox proportional hazards regression models will be applied in in each treatment group compared to phenprocoumon (reference) to estimate crude and confounder adjusted hazard ratios (HRs) of the above mentioned outcomes as well as treatment discontinuation (persistence) with accompanying 95% confidence intervals and *p*-values. Persistence (risk of non-persistence) will also be calculated separately for specific time points of interest (months 3, 6, 9, 12, 18 and 24). In the analysis of reduced vs. standard dose of NOACs, the standard dose will be used as reference. Kaplan-Meier cumulative incidence plots will be generated to characterize risk of outcome events of interest over time.

Information on confounding factors which are planned to be included in the models as well as in the estimation of the propensity score can be found in section 9.3.3.

In a second step, we will use the stabilized inverse probability of treatment weighting (IPTW) approach based on the propensity score to adjust for potential confounding resulting from imbalances in the baseline characteristics of different treatment groups. The objective of IPTW

based analysis is to create a weighted sample, for which the distribution of possible confounding variables is approximately the same between comparison groups (12,13). The propensity score is defined as the patient's probability to receive a treatment under investigation (i.e. phenprocoumon for main analyses and standard dose for the analyses of reduced vs. standard dose of NOACs) given a set of known patient's baseline characteristics. Propensity scores will be calculated using multiple logistic regression on a relevant set of patient characteristics listed in section 9.3.1 for each 1:1 comparison separately, e.g. rivaroxaban vs. phenprocoumon, rivaroxaban 15 mg vs. rivaroxaban 20 mg etc.

Let Z be an indicator variable relating to the treatment received by a patient, Z = 1 for an active treatment (e.g. rivaroxaban), Z = 0 for a control treatment (warfarin), and let X denote a vector of observed patient baseline characteristics. Then the propensity score is e = P(Z = 1|X). The inverse

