K27.4, K27.6, K28.0, K28.2, K28.4, K28.6, K29.0, K62.5, K66.1 K92.0, K92.1. K92.2, M25.0, N02, N42.1, N83.6, N85.7, N89.7, N93.0, N93.8, N93.9, N95.0, R04.0, R04.1, R04.2, R04.8, R04.9, R23.3, R31, R58, S06.4, S06.5, S06.6, S06.8

Section 9.3.3. Covariate definition

Operational definition of CHA2DS2-VASc Score:

Conditions	ICD-10 GM code	Assigned weights
Hypertension	I10 – I15, I67.4	1
Diabetes mellitus	E10 – E14	1
Heart failure	I11.0, I13.0, I13.2, I25.5, I42, I43, I50, I09.9	1
Age between 65 and 74 years		1
Vascular disease (previous MI, peripheral arterial disease or aortic plaque)	I21 – I23, I25.2, I70.0, I70.2 – I70.9, I71, I73.9	1
Stroke or TIA	G45.0 – G45.2, G45.4 – G45.9, I63, I69.3, I69.4, I64	2
Age \geq 75 years		2
Female sex		1

Operational definition of CHADS₂ Score:

Conditions	ICD-10 GM code	Assigned weights
Hypertension	I10 – I15, I67.4	1
Diabetes mellitus	E10 – E14	1
Heart failure	I11.0, I13.0, I13.2, I25.5, I42, I43, I50, I09.9	1
Stroke or TIA	G45.0 – G45.2, G45.4 – G45.9, I63, I69.3, I69.4, I64	2

Age ≥ 75	years
---------------	-------

1

Operational definition of modified HAS-BLED Score:

Criteria	ICD-10 GM / ATC /OPS code	Assigned weights
Hypertension	I10 – I15, I67.4	1
Liver or renal disease	B18.0, B18.1, B18.2, I85, K70.0, K70.2, K70.3, K70.4, K70.9, K72.1, K73, K74, K75.4, K75.8, K76.0, K76.6, K76.9, Z94.4, D63.1, E10.2, E11.2, E13.2, I12, I13, N02, N03, N04, N05, N07, N08, N14, N18.1-N18.4, N18.9, N19, Q61	1
Stroke history	I63, I69.3, I69.4, I64	1
Major bleeding event	OPS: 8800 ICD-GM: D62, H21.0, H31.3, H35.6, H43.1, H45.0, I32.1, I60 - I62, J94.2, M25.0, S06.4, S06.5, S06.6, S06.8	1
Alcohol abuse	F10	1
Non-steroidal anti-inflammatory drugs or antiplatelet	B01AC, M01A*	1
Age >65		1

Operational definition of claims based frailty indicator (10):

Criteria	ICD-10 GM / ATC /OPS code	Assigned weights
Impaired mobility	U50, Z99.3	1
Depression	F31, F32 – F34, F39, F43.1, F43.2,	1
Congestive heart failure	I11.0, I13.0, I13.2, I25.5, I42, I43, I50	
Parkinson's disease	G20-G22	

White race (yes vs. no)	N/A	
Arthritis (any type)	M05, M06, M08, L90.0, L94.0, L94.1, L94.3, M32 – M35, M45, M46, M48, M49	
Cognitive impairment	F01 – F05, F06.0, F06.7, F06.8, F07.0, F07.8, F09, G30, G31.0, G31.1, G31.8, R41	
Charlson comorbidity index (>0, 0)	As defined above	
Stroke	I60-I64, I69.0-4	1
Paranoia	F06.0, F06.2, F20, F22-F29, F32.3, F33.3, F44.8	
Chronic skin ulcer	170.24, 170.25, 183.0, 183.2, 187.21, L89, L97	
Male (yes vs. no)		

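### The adjustment list in section 9.3.3 leaves out the frailty indicator and nine of its components, so the reduced- versus standard-dose comparison is open to residual confounding by frailty of unknown size

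*Protocol*

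**What the plan says.** **Frailty.** Section 9.3.4 lists frail patients as a subgroup to be analysed with a test for effect modification. It says that "the recently validated claims based Frailty Indicator (10) will be used in this study" and fixes a threshold: "The frailty cut-off for this study will be 0.25 as the desire is to specifically identify frail individuals". No sentence in the protocol body puts the indicator into a model. For cancer, by contrast, the same section says explicitly that cancer types are added as covariates within that subgroup.

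**Adjustment set.** Section 9.7.2 refers to section 9.3.3 for "Information on confounding factors which are planned to be included in the models as well as in the estimation of the propensity score". Two paragraphs later it says that propensity scores are estimated "using multiple logistic regression on a relevant set of patient characteristics listed in section 9.3.1". Section 9.3.1 is the exposure definition and lists no patient characteristics.

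**Annex 3.** The code list for the frailty indicator stands under the heading "Section 9.3.3. Covariate definition", directly after CHA2DS2-VASc, CHADS2 and the modified HAS-BLED, which are all in the 9.3.3 list.

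**Comparison most exposed.** Section 8.3 plans to compare patients "initiating treatment with reduced dose of individual NOACs (rivaroxaban, apixaban, edoxaban) compared to standard dose in a subpopulation of patients without renal impairment" on IS/SE, severe IS, fatal bleeding and ICH. Section 9.7.2 applies all three approaches to it: adjusted Cox regression, stabilized IPTW and 1:1 propensity score matching.

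**The concern.** General frailty is a plausible reason to start a patient on the reduced dose, and it plausibly predicts stroke, bleeding and death. Where renal impairment is removed by restriction, frailty becomes relatively more important among the remaining reasons for dose choice. This is inference; the protocol does not say what drives dose choice.

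If frailer patients cluster in the reduced-dose group and the models do not fully capture frailty, the reduced dose will look less effective or less safe than it is. Section 7 raises the possibility that off-label dose reduction lowers effectiveness, and frailty confounding would push the hazard ratio the same way. Two of the outcomes, severe IS and fatal bleeding, use death in their definitions (section 9.3.2).

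The three methods do not check each other here. They draw on the same covariate list, so agreement among them says nothing about a confounder missing from it.

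**Working it through.** **Step 1: which list governs.** Section 9.7.2 gives two pointers. The one to 9.3.1 leads to no covariates and is a wrong cross-reference. The operative list is 9.3.3, and it does not name frailty.

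Annex 3 does not settle the matter. Its 9.3.3 part also defines renal impairment, systemic embolism, acute kidney injury and beta blockers, none of which is named in the 9.3.3 list. Standing under that heading is therefore not evidence of adjustment.

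**Step 2: the 21 rows of the indicator against the 9.3.3 list.**

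| Status | Rows | Count |
|---|---|---|
| Full or partial counterpart | depression, heart failure, arthritis, cognitive impairment (as dementia), stroke, paranoia (as psychosis), sex, age, hospital admission (as number of hospitalizations) | 9 |
| Marked not available in Annex 3 | white race, falls | 2 |
| Covered only indirectly, through single comorbidities | Charlson index | 1 |
| No counterpart | impaired mobility, Parkinson's disease, chronic skin ulcer, skin/soft tissue infection, mycoses, pneumonia, gout, musculoskeletal problems, urinary tract infection | 9 |

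9 + 2 + 1 + 9 = 21. A few single codes in the last group recur in listed covariates (for example G45 and M46 in the musculoskeletal row), but no listed covariate represents those rows. Section 9.3.3 also contains number of different medications and number of physician visits, which act as further proxies for frailty.

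**Step 3: possible size.** The protocol gives no frailty prevalence by dose and no frailty effect, so every input here is assumed. For an omitted binary confounder with prevalence p1 on reduced dose, p0 on standard dose and hazard ratio h, the bias factor on the reported hazard ratio is

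(1 + p1(h − 1)) / (1 + p0(h − 1)).

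*No help from proxies*, p1 = 30–50%, p0 = 15–20%, h = 1.3–2.0:
- smallest: p1 = 0.30, p0 = 0.20, h = 1.3 gives 1.09/1.06 = 1.03
- largest: p1 = 0.50, p0 = 0.15, h = 2.0 gives 1.50/1.15 = 1.30

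*Listed proxies cut the imbalance to 22–30% versus 20%*, h = 1.2–2.5:
- smallest: p1 = 0.22, h = 1.2 gives 1.044/1.040 = 1.00
- largest: p1 = 0.30, h = 2.5 gives 1.45/1.30 = 1.12

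The second scenario uses a wider range for h. With h = 1.3–2.0, as in the first, it gives 1.066/1.060 = 1.01 to 1.30/1.20 = 1.08.

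**Step 4: would the planned balance check show it?** The standardized mean difference is (p1 − p0)/√[(p1(1 − p1) + p0(1 − p0))/2]. The binary formula in 9.7.2 carries an extra factor of 100, left out here so that the result can be read against the 0.1 threshold. For p0 = 0.20:
- p1 = 0.22: 0.02/0.407 = 0.05
- p1 = 0.25: 0.05/0.417 = 0.12
- p1 = 0.30: 0.10/0.430 = 0.23

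The protocol's own threshold would separate the harmless case from the others, but only if frailty is in the balance tables.

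**Step 5: what the smallest comparison can bear.** Table 3 assumes one year of follow-up per patient. For edoxaban it gives 1,600 × 0.004 = 6.4 ICH events (shown as 6) and 1,600 × 0.022 = 35.2 IS/SE events (shown as 35). Both figures are before any split by dose or restriction by renal status.

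**The case against.** The strongest reply is that frailty is largely adjusted for already. Age, sex, hospitalizations, medication count, physician visits, dementia, depression, psychosis, heart failure, arthritis and stroke/TIA are all listed, and Annex 3 files the indicator as a 9.3.3 covariate. In addition, sections 9.7.2 and 9.9 acknowledge residual confounding, the dose comparison sits below the primary and secondary objectives, the abstract rules out confirmatory interpretation, and a more detailed SAP is to follow.

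Much of this stands. A reader might infer that the dose comparison is confounded outright, or that frailty is certainly unadjusted. The documents support neither: the proxies may remove most of the imbalance, and the Annex 3 heading leaves the intention unclear. Nor is hospital admission a gap, since the number of hospitalizations in the baseline year largely covers it. Section 8.3 is also ambiguous about its population, naming the overall population and patients with renal impairment as well as those without, so removal of renal impairment by restriction is one reading of it.

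Three things do not go away. The list to which 9.7.2 points is fixed in the protocol, so a SAP that follows it inherits the omission. The limitation in 9.9 concerns factors that claims data cannot measure adequately, whereas this indicator is one the study plans to compute. And nine components have no counterpart in the list.

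**Conclusion.** The point holds as a gap in the adjustment list and an inconsistency between 9.3.3, 9.7.2 and Annex 3. It should be corrected before analysis. The consequence is possible residual confounding by frailty, mainly in the reduced- versus standard-dose comparison. The NOAC versus phenprocoumon contrasts use the same list and are affected too, probably less.

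The size cannot be determined from the protocol. The illustration runs from about 1.00–1.12 with effective proxies to 1.03–1.30 with none, and no input comes from the document. Direction and relevance rest on two inferences: that frail patients more often start on the reduced dose, and that frailty carries risk beyond the listed covariates.

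**What to change.** 1. In 9.3.3, add the nine unlisted baseline frailty items as separate indicators, so that they enter every propensity score. Using items rather than the total score makes the adjustment independent of how the score and its cut-off are applied.
2. Add them to the Cox models where event counts allow. In sparse comparisons such as edoxaban, use them through the propensity score only.
3. Report the standardized mean differences of these items after weighting and after matching.
4. Align Annex 3 with 9.3.3, so that it is clear which defined items are adjustment covariates and which serve only subgroups.
5. Correct the pointer in 9.7.2 from section 9.3.1 to section 9.3.3.

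The codes are already in Annex 3 and the items must be extracted for the frailty subgroup, so no new data are needed. The price is slightly more variable weights and fewer matched pairs in small comparisons.
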